### **Methods:**

The ventilation protocol consisted in volume-controlled mechanical ventilation through Servo I Ventilator, inspiratory to expiratory ratio of 1:2, and a respiratory rate adjusted to normocapnia (end-tidal carbon dioxide partial pressure between 30 and 40 mmHg). Patients were randomly assigned to Standard (SV) or Protective (PV) group. Patients in the SV group received a Vt of 10 ml/kg of Ideal Body Weight (IBW) and a PEEP of 5 cmH2O, patients in the PV group a Vt of 6 ml/kg of IBW and a PEEP of 8-10 cmH2O, associated to recruitment maneuvers (RMs). IBW was calculated according to a predefined formula:  $50 + 0,91(\text{height [cm]} - 152,4)$  for men and  $45,5 + 0,91(\text{height [cm]} - 152,4)$  for women [16]. RMs were performed only in hemodynamic stable conditions and at pre-set moments: after the induction of anesthesia, after any disconnection from the mechanical ventilator, each hour during the surgical procedures and immediately before extubation. RMs were performed in Pressure Control mode as follows: the limit of peak inspiratory pressure was set at 45 cmH2O and the pressure control was set at 30 cmH2O, therefore three consecutive thirty seconds lasting inspiratory pauses were performed. At the end of RMs, respiratory rate, inspiratory to expiratory ratio, inspiratory pause, and Vt were set back at values preceding the RMs.

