### **Statistical Analysis:**

All data are expressed as mean  $\pm$  standard deviation (DS). We use the 2 –side T tests to compare the respiratory variables and gas exchange between the two groups tested. The analysis of variance for repeated measures in each group was performed by one-way ANOVA. When detected, post hoc

analysis was performed using Bonferroni Test. P values  $\leq 0,05$  were considered statistically significant.

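### The analysis over time names one-way ANOVA for repeated readings without a patient factor, sphericity handling, paired post hoc tests or a group-by-time test

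*Combined protocol and SAP*

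**What the plan says.** The Statistical Analysis section of the combined protocol and SAP sets out three steps.

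- Between groups: "We use the 2 –side T tests to compare the respiratory variables and gas exchange between the two groups tested".
- Over time: "The analysis of variance for repeated measures in each group was performed by one-way ANOVA".
- After a detected effect, the post hoc "analysis was performed using Bonferroni Test".

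The significance threshold is 0.05. The Methods section establishes two randomised groups: "Patients were randomly assigned to Standard (SV) or Protective (PV) group".

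The documents do not state the number of patients, the times of the readings, the error term of the ANOVA, any check or correction for sphericity, or whether the post hoc comparisons are paired. Methods gives times for the recruitment manoeuvres, but none for the readings. No test compares the time course between the groups.

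**The concern.** Readings on one patient are correlated. A test of change over time should therefore use within-patient variation as its error. The sentence mentions repeated measures but then names one-way ANOVA, which leaves two procedures open.

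- **Ordinary one-way ANOVA on the readings.** Differences between patients go into the error term, although the time effect varies only within patients. Real changes during the operation could be missed, and post hoc tests built on the same pooled error share the loss.
- **One-way repeated-measures ANOVA with time as the factor.** The patient is removed from the error, but the F test assumes sphericity. Readings close together in an operation plausibly correlate more than distant ones. If so, an uncorrected test rejects too often.

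Under either procedure the ANOVA is run separately in each group. A significant time effect in one group and not in the other is not evidence that the strategies change differently, and the plan contains no test of that. The introduction argues that pneumoperitoneum and head-down position impair respiratory function during surgery, so the course over time bears directly on the study's question.

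**Working it through.** **Inputs from the documents.** Two groups, a separate ANOVA in each, Bonferroni post hoc tests, and a nominal level of 0.05. The plan has no sample-size or power figure to reproduce.

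**Assumed inputs.** n = 20 patients per group, k = 2 to 6 readings, within-patient correlation ρ from 0 to 0.9. Two patterns were used: equal correlation (sphericity holds) and AR(1), where correlation falls with distance in time (sphericity fails if k is 3 or more).

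**Why ordinary one-way ANOVA is conservative.** With equal correlation, variance σ² and no time effect:

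- expected mean square for time = σ²(1 − ρ);
- expected error mean square without a patient term = σ²;
- expected error mean square with a patient term = σ²(1 − ρ).

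Without the patient term the F ratio therefore centres near 1 − ρ instead of 1: 0.5 at ρ = 0.5 and 0.1 at ρ = 0.9. For a post hoc difference between two times, the true variance is 2σ²(1 − ρ)/n and the pooled version is 2σ²/n. The standard error is too large by 1/√(1 − ρ), which is 1/√0.5 = 1.41 at ρ = 0.5 and 1/√0.2 = 2.24 at ρ = 0.8.

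**Type I error by simulation.** Multivariate normal data, no time effect, 20,000 replicates per setting; simulation standard error at 5% is √(0.05 × 0.95/20,000) = 0.0015. The error degrees of freedom are k(n − 1) for the ordinary test and (k − 1)(n − 1) for the repeated-measures test. Greenhouse-Geisser multiplies both degrees of freedom of the latter by the estimated ε. Entries are per cent at ρ = 0.5 / 0.7 / 0.9, n = 20.

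| Test and pattern | k = 3 | k = 4 | k = 5 | k = 6 |
|---|---|---|---|---|
| Ordinary, equal correlation | 0.4 / 0.0 / 0.0 | 0.3 / 0.0 / 0.0 | 0.2 / 0.0 / 0.0 | 0.2 / 0.0 / 0.0 |
| Ordinary, AR(1) | 1.0 / 0.2 / 0.0 | 1.4 / 0.3 / 0.0 | 1.7 / 0.7 / 0.0 | 2.3 / 0.9 / 0.0 |
| Repeated measures, equal correlation | 5.2 / 4.9 / 4.9 | 4.9 / 4.8 / 5.5 | 5.0 / 5.4 / 4.8 | 4.7 / 5.1 / 5.0 |
| Repeated measures, AR(1), uncorrected | 5.4 / 5.7 / 5.8 | 5.9 / 6.3 / 7.3 | 6.1 / 7.2 / 8.3 | 6.5 / 7.7 / 9.4 |
| Repeated measures, AR(1), Greenhouse-Geisser | 4.7 / 4.7 / 4.7 | 4.5 / 4.5 / 4.9 | 4.3 / 4.7 / 4.9 | 4.1 / 4.4 / 4.9 |

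At lower correlation the ordinary test is less affected: about 1% to 3% at ρ = 0.3, and nominal at ρ = 0. With k = 2 the repeated-measures test gives 4.8% to 5.2% throughout, because sphericity cannot fail. Results for n = 15 and n = 30 at k = 4 are similar.

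**Power.** n = 20, k = 5, time means (0, 0.5, 0.5, 0.5, 0) in SD units, ρ = 0.5 / 0.7 / 0.8:

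| Pattern | Ordinary one-way | Patient term, uncorrected | Patient term, Greenhouse-Geisser |
|---|---|---|---|
| Equal correlation | 30 / 23 / 19% | 77 / 95 / 99% | 73 / 94 / 99% |
| AR(1) | 37 / 30 / 24% | not given, as its level is inflated | 53 / 69 / 85% |

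**The case against.** The strongest reply is that the sentence itself refers to repeated measures. With one group at a time and time as the only factor, one-way most naturally describes one-way repeated-measures ANOVA. That stands, and it means the large losses above belong to the less natural reading.

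A reader might go further and infer that the error rate is wrong whichever test was meant. The documents do not support that. Repeated-measures ANOVA holds its level under sphericity and always with two readings, and the plan does not give the number of readings. Nor do the documents say that no correction was used; they are silent. Where sphericity does fail, the excess is modest in the cases run.

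A reader might also infer that the comparison of the two strategies is undermined. It is not: the between-group t tests do not use this error term. The lack of a group-by-time test limits what can be claimed about differing time courses, but it is not an error-rate fault of the ANOVA.

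Finally, every quantity behind the percentages is assumed, and the severity under the ordinary test depends on the correlation. That also stands. What the objection does not remove is the gap itself: the sentence permits two tests whose power in the equal-correlation example differs between 19% to 30% and 77% to 99%.

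**Conclusion.** The concern holds as a gap in specification with conditional consequences, under the assumed n = 20.

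- **If run as ordinary one-way ANOVA**, with correlation of about 0.5 or more, the time test has a type I error of about 0% to 2% and loses much of its power.
- **If run as repeated-measures ANOVA**, it is sound under sphericity or with two readings. Under AR(1) with correlation 0.5 to 0.9 and no correction, it rejects at about 5.5% to 6% with 3 readings and about 6% to 9% with 4 to 6.
- **Under either**, the plan cannot show that the two strategies differ in their course over time.

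The affected results are the within-group time tests and their post hoc comparisons. This should be settled before those tests are interpreted. It does not call the between-group t tests into question.

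**What to change.** State the reading times and replace the ANOVA sentence with one of the following.

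(a) *Each variable will be analysed by repeated-measures ANOVA with patient as a factor, time within patients and group between patients, including a group-by-time test. Tests involving time will use the Greenhouse-Geisser correction. Post hoc comparisons between times will be paired and Bonferroni-adjusted.*

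(b) *Each variable will be analysed in one linear mixed model over both groups with group, time and group-by-time as fixed effects, an unstructured within-patient covariance and Kenward-Roger degrees of freedom. Within-group changes will be Bonferroni-adjusted contrasts from this model.*

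A patient random intercept alone should not be offered as an equivalent to (b). It implies equal correlation. Its group-by-time test under AR(1) with 20 per group rejected at 5.7% (4 readings, ρ = 0.5) to 9.1% (6 readings, ρ = 0.9), the same inflation as the uncorrected ANOVA.

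If the analysis has already been run, the report should say which test was used, and the time analysis should be repeated in form (a) or (b).

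The cost is two or three sentences and a few lines of code, with no new data. The statistical price falls on (a) when sphericity does hold: the corrected test is then slightly conservative (type I error about 3% to 5%) and loses a few points of power, for example 73% instead of 77% at ρ = 0.5.

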**Effects on Respiratory mechanics of two different ventilation strategies during roboticgynecological surgery.**

**Introduction:**

For many years, the mechanical ventilation during general anesthesia has been conducted using high tidal volumes ( $V_t$ ) and without applying Positive End Expiratory Pressure (PEEP). This ventilatory strategy was considered to avoid alveolar collapse to improve ventilation-perfusion mismatch and to reduce the oxygen fraction. The potential harmful effects of short term intra-operative ventilation are increasingly recognized [1]. The mechanical ventilation may cause a pulmonary complication defined Ventilator-Induced Lung Injury (VILI). This respiratory condition is characterized by alveoli overdistension or repetitive opening and closing of atelectatic lung area. Alveolar overdistension could be prevented applying lower  $V_t$  [2] and higher levels of PEEP could prevent alveolar derecruitment [3]. Recently, two conventional meta-analyses of observational studies and randomized controlled trials on intra-operative ventilation have supported the use of lung protective ventilation, with lower  $V_t$  and higher levels of PEEP in order to prevent VILI and postoperative pulmonary complications [4,5]. Further studies are necessary to understand if the outcome improvement was related to lower  $V_t$  or high levels of PEEP. Laparoscopy is a well-established procedure for gynecologic surgery, with an induced pneumoperitoneum to facilitate the laparoscopic manipulation and it is often performed in Trendelenburg position (the head down body position). The increase of abdominal pressure related to both pneumoperitoneum and Trendelenburg position has demonstrated to impair the respiratory function, mainly inducing atelectasis area in the dependent lung regions [6-9]. In case of atelectasis, the distribution of  $V_t$  to the limited amount of functional lung parenchyma may induce alveolar stress and strain. These conditions are the main mechanisms underlying VILI [10-11] and the hypothesis that a protective ventilation has some benefits and should be applied during general anesthesia has been widely demonstrated [6,9,12-15]. Recently, the concept of “lung protective ventilation strategy” has been adapted from acute respiratory distress syndrome to the anesthesiologic management. In fact, the application of an “open lung” strategy, consisting in a recruitment maneuvers (RMs) followed by the consequent application of PEEP has been suggested to be able to improve oxygenation through the re-expansion of pneumoperitoneum-induced atelectasis area. The effects of open lung

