
ventilatory strategy on respiratory mechanics and postoperative pulmonary complications in healthy patients underwent robotic–laparoscopic surgery in deep Trendelenburg position have not been specifically investigated. The aim of this study was to evaluate the effects of two ventilatory strategies (protective mechanical ventilation versus conventional mechanical ventilation), during general anesthesia in robotic laparoscopic gynecological surgery in deep Trendelenburg position, on respiratory mechanics and postoperative pulmonary complications in healthy patients.

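### Holm's step-down procedure could replace Bonferroni for the within-group time contrasts at no cost in family-wise error; the power gained cannot be computed from the documents and does not touch the between-group comparison

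*Combined protocol and SAP*

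**What the plan says.** The Statistical Analysis section has two inferential parts. Between groups: "We use the 2 –side T tests to compare the respiratory variables and gas exchange between the two groups tested". Within groups: "The analysis of variance for repeated measures in each group was performed by one-way ANOVA", and where that detects a difference, the post hoc "analysis was performed using Bonferroni Test. P values" at or below 0.05 count as significant. No step-down version is named, so the ordinary reading is single-step: each of m contrasts is tested at 0.05/m.

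The Introduction gives a reason to expect change over the course of surgery: "The increase of abdominal pressure related to both pneumoperitoneum and Trendelenburg position has demonstrated to impair the respiratory function". It states no size for that change. The documents give no measurement times, number of contrasts, patients per group, SD, within-patient correlation or effect size. The aim, at the end of the Introduction, is a comparison of two ventilatory strategies, so the within-group time contrasts are supportive.

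**The concern.** Single-step Bonferroni holds every contrast to the level 0.05/m, however many of the others have clearly been rejected. Holm's procedure relaxes the level as contrasts are rejected. If readings taken under pneumoperitoneum and Trendelenburg differ strongly from those taken before and after, those contrasts reject easily. The remaining ones, such as drift during pneumoperitoneum or return to the starting value, are then tested more strictly than the 5% limit requires. At stake is some power in one of only two planned inferential analyses, with no change reported somewhat more often than necessary. False-positive risk is not at stake, because Bonferroni protects against it.

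**Working it through.** The plan states no power or sample-size figure, so there is nothing to reproduce. The check has a part that needs no assumptions and a part that rests on them.

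**1. Holm never rejects fewer contrasts.** Holm orders the P values and compares them with 0.05/m, 0.05/(m−1), …, 0.05/1, stopping at the first failure. Every threshold is at least 0.05/m, so any contrast with P ≤ 0.05/m is rejected by both methods.

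**2. Holm keeps the same limit.** Let m₀ contrasts be truly null. When the first true null is reached, at least m₀ contrasts are still in the list, so its threshold is at most 0.05/m₀. By the Bonferroni inequality, the chance that any true null falls below 0.05/m₀ is at most m₀ × 0.05/m₀ = 0.05. No independence is needed.

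**3. What the gain depends on.** With r contrasts already rejected, the next is tested at 0.05/(m−r) instead of 0.05/m. For a contrast with 50% power under Bonferroni (normal approximation), power at the next Holm step is Φ(z₀.₅₀ + z(0.05/m) − z(0.05/(m−r))), where z(a) is the two-sided critical value at level a:

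| Readings | m | r | Bonferroni level | Holm level | Power under Holm |
|---|---|---|---|---|---|
| 3 | 3 | 1 | 0.0167 | 0.0250 | 56% |
| 4 | 6 | 1 | 0.0083 | 0.0100 | 52.5% |
| 4 | 6 | 4 | 0.0083 | 0.0250 | 65% |
| 5 | 10 | 6 | 0.0050 | 0.0125 | 62% |
| 6 | 15 | 10 | 0.0033 | 0.0100 | 64% |

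With r = 0 there is no gain at the first step.

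**4. Illustration over a range of stage effects.** All inputs are assumed: 5 readings (m = 5 × 4/2 = 10), 20 patients per group, SD 1, within-patient correlation 0.6, paired t tests, and true means (0, −s, −s, −s, −0.5), where s is the stage shift. The contrast of interest is first versus last. Its SD is √(2 × (1 − 0.6)) = 0.894, so its paired effect is 0.5/0.894 = 0.56.

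- Noncentral t with n = 20 and effect 0.56: power is 28.7% at 0.05/10 = 0.005 and 42.0% at 0.05/4 = 0.0125. The second level applies when the six stage contrasts are rejected first.
- Simulated power on this contrast (at least 20,000 trials per row):

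| Stage shift s | Bonferroni | Holm |
|---|---|---|
| 2 SD | 29% | 42% |
| 1 SD | 29% | 35–36% |
| 0.8 SD | 29% | 34% |
| 0.5 SD | 29% | 31% |
| 0.3 SD | 29% | gain under 1 point |

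Holm lost none of Bonferroni's rejections in these runs. At s = 2, where three contrasts are truly null, family-wise error was about 1.5% for Bonferroni and 4.0% for Holm.

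**5. Not modelled.** The ANOVA that precedes the post hoc step was not simulated. The plan also does not say whether the post hoc tests are paired or use the pooled ANOVA error. With pooled error, Bonferroni power in step 4 would be about 35% instead of 29%.

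**The case against.** The plan names a valid correction, and a preference for Holm could be expressed about almost any trial that uses Bonferroni. That stands: this is a refinement.

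A reader might infer from the Introduction that several stage contrasts are almost certain to be rejected, and hence that the plan loses a known and sizeable amount of power. The documents do not support this. They give a direction and no magnitude, and the assumed stage shift decides the result: the gain in the illustration runs from 13 points down to less than 1. The Introduction also suggests that recruitment followed by PEEP may reverse part of the atelectasis, so stage effects on oxygenation in the protective arm could be smaller.

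A reader might also infer that the relaxed contrasts show what each strategy does. They do not. A change over time within one arm mixes the strategy with surgery, position and duration of anesthesia, which both arms share. The documents do not single out drift or return to baseline as questions of interest. More within-arm rejections could even encourage the invalid argument that one arm changed and the other did not.

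Finally, Holm spends more of each family's 5%, and the plan states no control across variables or arms. With 10 independent families (assumed: 5 variables × 2 arms), the chance of at least one false claim is 1 − (1 − 0.015)¹⁰ ≈ 14% under Bonferroni and 1 − (1 − 0.040)¹⁰ ≈ 34% under Holm, using the step 4 error rates. Each family stays within its limit, but this is a real trade-off.

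None of this removes the basic fact that, within a family, Holm dominates Bonferroni at the same stated limit.

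**Conclusion.** The point holds as a small, optional improvement. That Holm rejects at least as much as Bonferroni at the same 5% limit within a family holds without assumptions. The size of the gain does not follow from the documents. Under the stated assumptions it is about 13 points of power at a 2 SD stage shift, 6 to 7 at 1 SD, 5 at 0.8 SD, 2 at 0.5 SD and under 1 at 0.3 SD. The present method is not an error. The change adds nothing to the between-group t tests, which address the trial's aim.

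**What to change.** In the Statistical Analysis section, replace the reference to the Bonferroni test with: *Holm's step-down Bonferroni procedure applied to the within-patient comparisons between time points*. This needs no new data and is available in standard software. The wording also settles that the comparisons are paired within patient, which the plan leaves open.

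There are two small costs. Simultaneous confidence intervals that match Holm's tests are less simple than Bonferroni's, although the section plans none. Each family will also use more of its 5% allowance, with nothing stated across variables or arms. A sentence saying that within-group results are descriptive of each arm and are not a comparison of the strategies would guard against misreading.
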